7.3. Clinical Laboratory Analyses

Laboratory evaluations including the analyses of Chemistry laboratory tests, Hematology laboratory tests, Urinalysis, Renal and Liver function tests will be based on GSK Core Data Standards. The details of the planned displays are in **Error! Reference source not found.**: List of Data Displays.

7.4. Other Safety Analyses

The analyses of non-laboratory safety test results including vital signs, 12 lead ECG and 24-hour telemetry will be based on GSK Core Data Standards, unless otherwise specified. The details of the planned displays are presented in **Error! Reference source not found.**: List of Data Displays.

8. PHARMACOKINETIC ANALYSES

All PK analyses planned for the study are a part of the secondary objectives.

8.1. Statistical analyses of derived PK parameters

8.1.1. Endpoints / Variables

8.1.1.1. Drug Concentration Measures

Refer to [Appendix 5](#): Data Display Standards & Handling Conventions (Section 10.5.3 Reporting Standards for Pharmacokinetic).

8.1.1.2. Derived Pharmacokinetic Parameters

Pharmacokinetic parameters will be calculated by standard non-compartmental analysis according to current working practices and using the currently supported version of WinNonlin version 8.0. All calculations of non-compartmental parameters will be based on actual sampling times.

For dose escalation meeting and interim analysis planned sampling times may be used if actual timepoints are not available.

Pharmacokinetic parameters listed will be determined from the plasma concentration-time data, provided there is enough evaluable data available for the calculations. If the concentration data is available partially, then based on scientific judgement the data will be assessed for inclusion or exclusion from the analysis.

Parameter	Parameter Description
Plasma PK Parameters:	
Cmax	Maximum observed concentration, determined directly from the concentration-time data.
RCmax	Ratio of Cmax on last dose to Cmax on first dose, i.e., $RCmax = \frac{Cmax \text{ on the last dose}}{Cmax \text{ on the first dose}}$
Ctau	Trough concentration determined directly from the concentration data (only for Part B of the study). It will be the concentrations at 12h or 8h after first dose (if BID or TID administration, respectively) and always concentration at pre-dose on the last dose.
RCtau	Ratio of Ctau on last dose to Ctau on first dose, i.e., $RCtau = \frac{Ctau \text{ on the last dose}}{Ctau \text{ on the first dose}}$
tmax	Time to reach Cmax, determined directly from the concentration-time data.
tlag*	Lag time before first observation of drug concentrations (after single dose only)

Parameter	Parameter Description
Tlast*	Time of last quantifiable concentration
t _{1/2}	Apparent terminal half-life will be calculated as: $t_{1/2} = \frac{\ln 2}{\lambda_z}$ (NOTE: λ _z is the terminal phase rate constant).
AUC(0-24h)	Area under the concentration-time curve from time zero to 24 hours post-dose (after single dose only).
AUC(0-t)	Area under the concentration-time curve from time zero to the time of the last quantifiable concentration (C(t)) will be calculated using the linear trapezoidal rule for each incremental trapezoid and the log _e trapezoidal rule for each decremental trapezoid.
AUC(0-tau)	Area under the concentration-time curve from time zero to the time of the trough concentration (C(tau)) will be calculated for Part 2 of the study only (repeat dose) using the linear trapezoidal rule for each incremental trapezoid.
RAUC(0-tau)	AUC(0-tau) on last dose to AUC(0-tau) on first dose $RAUC(0 - \tau) = \frac{AUC(0 - \tau) \text{ on the last dose}}{AUC(0 - \tau) \text{ on the first dose}}$
AUC(0-∞)	Area under the concentration-time curve extrapolated to infinity will be calculated (after single dose only) as: $AUC(0 - \infty) = AUC(0 - t) + \frac{C(t)}{\lambda_z}$ (NOTE: λ _z is the terminal phase rate constant. % of the extrapolated area should not exceed 20%. Any value of AUC(0-∞) derived with more than 20% extrapolation should be flagged and excluded from summary statistics if >30%).
AR _{pred}	AR _{pred} is calculated as : $ARpred = \frac{1}{1 - e^{k * \tau}}$ where k is elimination rate constant following the single dose and tau is the dosing interval for the intended repeat dosing.
R ² adjusted*	The goodness of fit statistic for the terminal elimination phase, adjusted for the number of points used in the estimation of λ _z .
λ _z	λ _z is the terminal phase rate constant. A minimum number of three data points in the terminal phase will be used starting at any post-Cmax data point. The adjusted correlation coefficient (R ² adjusted) in general should be greater than 0.90. Any value < 0.90 but ≥ 0.8 will be flagged but may be used at the PK Scientist's best knowledge and judgment, any value <0.8 should be considered for exclusion from the statistical analysis. All the derived parameters that include λ _z in their calculation (i.e. t _{1/2} , AUC(0-∞)) will need to be flagged or excluded from statistical analysis accordingly. The interval used to determine λ _z should be equal or greater than 1.5-fold the estimated half-life or otherwise flagged and used at the PK Scientist's best knowledge and judgment.
λ _z upper limit*	The upper limit on time for values to be included in the calculation of λ _z .

Parameter	Parameter Description
λz lower limit*	The lower limit on time for values to be included in the calculation of λz
λz number of points*	The number of time points used in computing λz .
% AUC _{ex} *	Percent of AUC _∞ that is extrapolated beyond last quantified concentration
CL/F*	The apparent clearance will be calculated only for Part 1 of the study (single dose) as Dose/ AUC(0-∞)
CL _{ss} *	The apparent clearance at steady state will be calculated only for day 10 Part 2 of the study (repeat dose) as Dose/ AUC(0-tau)
Urine PK Parameters:	
$A_e(t_{1-tz})^*$	Amount excreted in the urine at each interval collection (24 h)
$f_e(0-tz)^*$	The fraction of unchanged drug excreted in urine will be calculated as $f_e = A_e/Dose$, up to tz hours, where tz is the last collection time
CL _R *	Renal Clearance calculated as $A_e(0-tz) / AUC_{(0-tz)}$.

NOTES:

- *Additional exploratory parameters have been included which will be listed only.

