### **5.5.5. Multiple Ascending Dose (MAD)**

Three dosing cohorts will be used for MAD. The selection of appropriate daily doses will be performed upon consideration of available safety, tolerability and PK data from SAD part and/or any preceding repeat dose cohorts in MAD and limiting exposure to be no less than 5-fold below the NOAEL of the rat 28-day toxicity study (AUC: 434  $\mu\text{g.h/mL}$ ,  $C_{\max}$ : 46.2  $\mu\text{g/mL}$ ). Twice-daily (BID) dosing is currently planned for MAD, but other dosing options may be considered based upon the safety/tolerability and pharmacokinetics observed in SAD part. For MAD dose selection, three doses based on exposures from SAD that support single/repeated dosing will be chosen identifying maximum anticipated therapeutic dose. Once this dose is identified, three cohorts will be chosen for the MAD doses: cohort 1 (0.5X anticipated therapeutic dose), cohort 2 (0.75X maximum anticipated therapeutic dose) and cohort 3 (maximum anticipated therapeutic dose). It should be noted that calculated steady state plasma  $AUC_{0-24h}$  exposure on day 10 will be used as part of PK stopping criteria following repeat dosing. PK sampling is proposed for 0-12h for BID dosing or 0-7h for TID dosing on day 10 at steady state; hence  $AUC_{0-24h}$  (day 10) will be derived as  $2 \times AUC_{0-12h}$  or extrapolated  $AUC_{0-8h} \times 3$  for BID or TID dosing, respectively.

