Study Treatment				X	X	X	X	X	X	X	X	X	X			
PK samples will be collected at the following time points:
 
Once-daily dosing:
 
Day 1: Pre-dose, 10min, 30min, 1hr, 1.5hr, 2hr, 2.5hr, 3hr, 4hr, 5hr, 6hr, 8hr, 10hr, 12hr
 
Days 2 – 9: Pre-dose PK samples collected
 
Day 10: Pre-dose, 10min, 30min, 1hr, 1.5hr, 2hr, 2.5hr, 3hr, 4hr, 5hr, 6hr, 8hr, 10hr, 12hr
 
Day 11: 24hr sample post-dose from Day 10.
 
TID dosing:
 
Day 1: Pre-dose, 10min, 30min, 1hr, 1.5hr, 2hr, 2.5hr, 3hr, 4hr, 5hr, 6hr, 7hr (pre-2nd dose)
 
Days 2 – 9: Pre-dose PK samples collected prior to the first-dose and second-dose
 
Day 10: pre-dose, then post first-dose at 10min, 30min, 1hr, 1.5hr, 2hr, 2.5hr, 3hr, 4hr, 5hr, 6hr, 7hr (pre-2nd dose).
 
The time points stated may be modified depending on emerging SAD PK profiles.
 
Blood volumes to be collected include 2 mL for post-dose 0-11 hrs, and 5 mL for post-dose 12-24 hrs.
 
Once daily dosing: GSK3186899 or placebo will be administered.
	

Procedure	Screening (Up to 28 days before Day 1)	Study Period (Days)													Follow-up (14-21 days post last dose) /Early Withdrawal	Notes	
		-2	-1	1	2	3	4	5	6	7	8	9	10	11	12	13	
																	TID dosing: GSK3186899 or placebo will be administered using a 7 hr dosing interval between each dose.
Meals		X	X	X	X	X	X	X	X	X	X	X	X	X	X		If on fed regimen (both once daily and TID dosing): On Day 1 through to D10, participants will receive an adapted standard meal 30 mins prior to dosing.  If on fasted regimen (once daily dosing): On Day 1 through to D10, participants will have fasted 8hr overnight prior to dose 1. A breakfast will be served approximately 2hr after dose 1. Lunch, dinner and other snacks may be served as per the site schedule.  If on fasted regimen (TID dosing): On Day 1 through to D10, participants will have fasted 8hr overnight prior to dose 1. A breakfast will be served approximately 2hr after dose 1. Lunch and dinner will be served between 2 hr prior to dose 2 and 3, respectively.  Participants will receive standardized meals scheduled at the same time in each period. Meals will be served as per the site schedule on Days -1 and Days 11-13.  8 fl oz (240mL) of water to be taken after dosing and permitted on an ad lib basis 1hr before and 1hr after dosing.

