
 To collect bile sample for analysis of metabolites of GSK3186899 (Part A fed regimen only) 	
 Metabolites of GSK3186899 in bile. These analyses will be detailed in a separate analysis plan.

* Accumulation ratios calculated as the ratio of last dose to first dose PK parameters: RAUC(0-tau) = AUC(0-tau) on last dose to AUC(0-tau) on first dose, RCmax = Cmax on last dose to Cmax on first dose, RCtau = Ctau on last dose to Ctau on first dose. # ARpred = 1/(1-e^(k*tau)) where k is elimination rate constant following the single dose and tau is the dosing interval for the intended repeat dosing.

† It is AUC(0-12) if dosing is BID, or, AUC(0-8) if dosing is TID.

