8.5.1. Endpoints/Variables

To assess the time invariance dose accumulation, the statistical analysis will be based on the ratio of AUC(0-tau) (i.e., AUC(0-12) if dosing is BID or, AUC(0-8) if dosing is TID) on day 10 to AUC(0-∞) on day 1, if data permits.

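### If TID is chosen for Part B, the SAP's 8 h rule for Ctau cannot be applied: doses are 7 h apart and serial sampling stops at 7 h, before the second dose

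*SAP*

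**What the plan says.** BID is the planned Part B regimen. SAP 2.3 keeps once-daily and TID dosing open, to be selected on Part A data, and SAP 10.2.2 sends the reader to protocol Appendix 5 for the sampling times of any non-BID regimen.

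**SAP definitions for TID**
- 8.1.1.2, source of Ctau: "Trough concentration determined directly from the concentration data (only for Part B of the study").
- 8.1.1.2, time of Ctau after the first dose: "It will be the concentrations at 12h or 8h after first dose (if BID or TID administration, respectively"). On the last dose, Ctau is always the pre-dose concentration.
- 8.1.1.2, AUC(0-tau): "Area under the concentration-time curve from time zero to the time of the trough concentration (C(tau")), which makes it AUC(0-8) under TID.
- 2.2, footnote on the time-invariance ratio: "It is AUC(0-12) if dosing is BID, or, AUC(0-8) if dosing is TID". Section 8.5.1 repeats this: "AUC(0-12) if dosing is BID or, AUC(0-8) if dosing is TID".

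**Protocol schedule for TID**
- Appendix 5, dosing: "GSK3186899 or placebo will be administered using a 7 hr dosing interval between each dose".
- Appendix 5, the serial samples on Days 1 and 10 end with "4hr, 5hr, 6hr, 7hr (pre-2 nd dose"). On Days 2-9, samples are drawn before the first and second doses only.
- 5.5.5: "PK sampling is proposed for 0-12h for BID dosing or 0-7h for TID dosing on day 10 at steady state". The same sentence derives the daily AUC for the PK stopping criterion as three times an extrapolated AUC0-8h.

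**The concern.** Eight hours is 24/3, but the protocol's TID day is not split evenly: doses at 0, 7 and 14 h leave a 10 h overnight gap. The SAP's 8 h point falls one hour after the second dose, and no sample is scheduled there. A Ctau that must come directly from the data therefore has no value on Day 1.

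The Day 10 side is also unclear. Read literally, the last dose under TID is the third dose on Day 10, and nothing is sampled before it. The available pre-dose samples are the morning one, which follows the 10 h gap, and the 7 h one, which follows a 7 h gap. Only the second matches a 7 h Day 1 value.

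RCtau is part of a secondary endpoint, and Ctau is also a dose-proportionality variable for Part B. Unless the rule is settled beforehand, the choice of sample would be made after Part B data exist.

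**Working it through.** **1. Schedule check.** SAP: Ctau at 8 h. Protocol: second dose at 7 h, last serial sample at 7 h. Under BID, both documents use 12 h and a 12 h sample is scheduled, so the conflict is confined to TID.

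**2. Inputs for size** (protocol 5.5.1, Table 3 and the Table 5 key): CL 438 mL/h/kg, V 800 mL/kg, 70 kg, ka 0.7 per h, F 0.5, blood-to-plasma ratio 0.60. Hence ke = 438/800 = 0.5475 per h. I use 600 mg per dose at 0, 7 and 14 h for 10 days; the ratios do not depend on dose.

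One-compartment oral model, single dose, plasma:
- C(t) = A(e^(−ke·t) − e^(−ka·t))
- AUC(0-t) = A[(1 − e^(−ke·t))/ke − (1 − e^(−ka·t))/ka]
- A = F·D·ka / [V(ka − ke)] / 0.60 = 0.5 × 600 × 0.7 / (56 × 0.1525) / 0.60 = 40.98 µg/mL

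**3. Model check against the protocol.** Half-life = ln 2/0.5475 = 1.27 h (stated ~1.3 h). AUC0-24h at 600 mg is 16.31 against 16.59 µg.h/mL in Table 5. Cmax is 3.70 against 3.28 µg/mL, about 13% high. The model is good enough for ratios, not for exact concentrations.

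**4. Day 1 Ctau.**
- C(7) = 40.98 × (0.02166 − 0.00745) = 0.582 µg/mL
- First dose extrapolated to 8 h: 40.98 × (0.01253 − 0.00370) = 0.362 µg/mL
- 0.362/0.582 = 0.62, so 38% below the 7 h trough

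**5. RCtau.** Day 10 morning pre-dose is 0.138 µg/mL (last dose 10 h earlier); Day 10 pre-second-dose is 0.586 µg/mL.

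| Day 10 numerator | Day 1 denominator | RCtau |
|---|---|---|
| Morning pre-dose | 8 h extrapolated | 0.138/0.362 = 0.38 |
| Morning pre-dose | 7 h sample | 0.138/0.582 = 0.24 |
| Pre-second-dose (7 h) | 7 h sample | 0.586/0.582 = 1.01 |

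The first two rows would look like a fall in exposure. They arise from comparing troughs after unequal gaps.

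**6. AUC(0-tau).** Day 1 AUC(0-7) = 15.12 and first-dose-only AUC(0-8) = 15.59 µg.h/mL, a difference of +3%. Day 10 AUC(0-7) = 15.38. For Day 10 AUC(0-8) without the second dose, subtract that dose's first hour from the as-dosed value: 17.94 − (17.67 − 15.59) ≈ 15.85.
- RAUC: 15.38/15.12 = 1.017 with 0-7 h; 15.85/15.59 = 1.017 with 0-8 h
- Time-invariance ratio, with Day 1 AUC(0-∞) = 16.31: 15.38/16.31 = 0.943 with AUC(0-7); 15.85/16.31 = 0.972 with extrapolated AUC(0-8)

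**7. Dose proportionality.** In the power model, log y = log α + β log(dose). Under linear PK, moving from 7 h to an extrapolated 8 h multiplies y by a constant, which changes α and leaves β alone.

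**8. Sensitivity to half-life.** With a purely log-linear tail, the fall from 7 h to 8 h is 1 − 2^(−1/t½): 41% at 1.3 h, and 13% at 5 h, the value at which SAP 10.4.1 would revise its phase definition. A longer half-life shrinks the Ctau gap and enlarges the AUC difference.

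**The case against.** The strongest reply is that 8 h is a deliberate convention. Protocol 5.5.5 acknowledges 0-7 h sampling under TID and still works with an extrapolated AUC0-8h. That stands for AUC: the missing piece is a sentence carrying the extrapolation into the SAP, since 5.5.5 applies it only to the stopping criterion. It does not rescue Ctau, which the SAP takes directly from the data.

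TID is also only a contingency: the SAP's Part B treatment labels are all BID. This stands and limits the weight of the point. PK times may be modified without an amendment, so an 8 h sample could be added, but with doses 7 h apart it would still follow the second dose.

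A reader might infer three stronger things that the documents do not support:
- **That Ctau would be about 6.4 times the trough, or AUC(0-tau) 17% too high, by mixing two doses.** The model does give 3.71/0.582 = 6.4 and 17.67/15.12 = 1.17 as dosed. Both need concentrations after 7 h, and none are scheduled.
- **That all repeat-dose PK analyses fail under TID.** RAUC and the dose-proportionality slope are essentially indifferent to 7 h or 8 h.
- **That AUC(0-7) should be imposed throughout.** This moves the time-invariance ratio further from 1 (0.943 against 0.972), departs from 5.5.5, and leaves the last-dose Ctau clause unresolved.

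**Conclusion.** The concern holds for Ctau and RCtau, conditional on TID being selected. As written, the SAP's rule points to an unsampled time after the second dose and cannot yield a trough. Depending on the improvised substitute, RCtau could be reported as about 0.24 to 0.38 when the like-for-like value is about 1.01. For AUC(0-tau) this is a gap in specification with an effect of about 3%.

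The mismatch between 8 h and 7 h is read straight from the documents. The sizes rest on the protocol's predicted typical-subject PK, linear kinetics and doses at 0, 7 and 14 h. SAP 2.3 records higher than expected exposures in Part A, so the observed values may differ. Under BID nothing changes.

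**What to change.** For TID only:

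1. In SAP 8.1.1.2, define Day 1 Ctau as the scheduled 7 h pre-second-dose sample.
2. Use the matching Day 10 pre-second-dose (7 h) sample as the RCtau numerator, in place of the clause that always takes the pre-dose value on the last dose.
3. State whether AUC(0-tau) is the observed AUC(0-7) or the extrapolated AUC(0-8), with the extrapolation rule if the latter, and use it the same way on Day 1 and Day 10. This must be explicit because 8.1.1.2 ties AUC(0-tau) to the time of Ctau: moving Ctau to 7 h would otherwise shift AUC(0-tau) silently and leave it at odds with 2.2 and 8.5.
4. Reconcile SAP 2.2, 8.1.1.2 and 8.5 with protocol 5.5.5 and Appendix 5 accordingly.

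The cost is a few lines of SAP wording, best settled before Part B data are available. No new samples are needed, and no change to the dosing interval is proposed.

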8.1.2. Summary Measure

All the derived PK parameters will be summarized descriptively.

Detail methods and displays of the summary measures are specified in Section 8.1.6 Statistical Analyses/ Methods.

Some of the parameters in the list above will be used for statistical modelling, as described in the subsequent analyses sections.

8.1.3. Population of Interest

These descriptive summaries will be based on the PK population.

8.1.4. Strategy for Intercurrent (Post-Randomization) Events

In Table 2 below, the possible intercurrent events and the rationale for relating them to treatment or otherwise is described. Once a subject discontinues from study treatment, they will proceed straight to follow up and no further data will be collected.

Individual subject data will be included in data listings regardless of the strategies followed for the analyses.

If feasible, subjects will be replaced until the desired sample size is attained.

Table 2 Strategies for Intercurrent events

Intercurrent events	Relation to treatment and rationale	Strategy, rationale and details of action taken
Subject withdraws study consent	
Not related to treatment/
 
Subject drops out due to logistic reasons and not due to any event related to treatment
	
 - The strategy will be a While-on-Treatment strategy, where we are interested in the treatment effects prior to the withdrawal only. - Subjects' data available up to the withdrawal will be included in the descriptive PK summaries. - If a subject withdraws consent during a period, the missing data post withdrawal will not be imputed. - The derived PK parameters for e.g., AUC, C_{max} etc. of that partially completed period will be calculated if data permits (See section 8.1.1.2 Derived Pharmacokinetic Parameters for details on derivation criteria).
Subject does not take the full treatment	
Not related to treatment/
 
The treatment will be administered as a powder dissolved in diluent. To ensure all treatment is ingested, the bottle containing the dispersion will be rinsed three times and the subject will be expected to ingest this in addition to the initial dispersion. If three rinses are not all ingested, the subject may not take the full treatment dose.
	
In the current formulation, it is hard to measure the exact proportion of dose ingested if not all rinses are taken. It is also uncertain whether the formulation could change in future development. To account for this, we propose two different strategies described below. If this intercurrent event is not observed, then both strategies will provide the same results and only the hypothetical strategy will be presented for the final analysis.
 
Primary analysis
 
 - The strategy will be a Hypothetical strategy, where we are interested in the treatment effects in a hypothetical scenario where all subjects have taken complete dose. - In this case, the data from a period in which an incomplete dose is taken would be considered as missing at random and excluded from analyses. - If the drug formulation is changed in the future studies, this estimate will provide the true relationship between the actual dose intake and its exposure under this strategy. 
Supplementary analysis
 
 - The strategy will be a Treatment policy strategy, where we are interested in the

		
treatment effects regardless of the actual amount of dose taken.
 
 - The analysis will include PK parameters derived based on concentrations of both complete and partial doses (if data permits based on criteria described in Section 8.1.1.2) and will be analysed using the nominal or prescribed dose. - If the drug formulation remains unchanged in the future studies, this estimate will provide the true relationship between a nominal dose and its exposure under this strategy, i.e., a close to real-world situation.
Subject drops out due to Adverse events	
Related to treatment/
 
If the adverse event is confirmed to be related to study treatment
	
 - The primary strategy will be a Hypothetical strategy, where we are interested in the treatment effects in a hypothetical scenario where discontinuation due to an AE would not happen. - The missing data after discontinuation will be assumed to be missing at random - The derived PK parameters of the last fully or partially completed period will be calculated if data permits (See section 8.1.1.2 Derived Pharmacokinetic Parameters for details on derivation criteria).

8.1.5. Statistical Analyses / Methods

For parameters tabulated in Section 8.1.2, data will be summarized using the following descriptive statistics.

- N, n, arithmetic mean, 95% confidence interval (CI) for the arithmetic mean, SD, median, minimum, maximum for the untransformed data
- Geometric mean, 95% CI for the geometric mean, SD of log_e-transformed data and %CV_b or %CV_w for the untransformed data (except Tmax and T_½)
- Based on the intercurrent events observed in the study, appropriate strategies from Table 2 in Section 8.1.4 will be considered for handling of missing data (if any) and interpretation of the analysis results. If multiple intercurrent events are observed (for e.g., if the subject does not take the full treatment as well he withdraws study consent), then the data will be handled using more than one strategy as described in Table 2 and interpretations of the results will be made accordingly.

Graphical presentations will be provided if appropriate. All data will be listed. Details of the planned displays are provided in **Error! Reference source not found.**: List of Data Displays and will be based on GSK Data Standards and statistical principles.

